Specific Aim 1: To determine whether ED and/or WMH moderate the difference in patient expectancy and antidepressant outcome between the open vs. placebo-controlled conditions. Hypothesis 1: Greater ED and WMH will be associated with smaller differences in expectancy and antidepressant outcome between conditions.

Specific Aim 2: To determine whether a loss of expectancy effects mediates the relationship between ED/WMH and poor antidepressant outcome. Hypothesis 2: ED and WMH will be associated with decreased change in depressive symptoms, and these associations will be mediated by a decreased contribution of expectancy to antidepressant outcome.

Exploratory Aim: To assess the integrity of frontostriatal and frontolimbic white matter tracts using DTI and explore whether specific damage to these pathways is associated with diminished expectancy effects in patients with LLD.

Substantiating this model would provide a mechanism explaining how ED and WMH predict non-response to antidepressant medications in LLD. Understanding the mechanisms of antidepressant non-response in LLD has the potential to yield treatments based on specific and rational designs that target the involved biological pathways. By combining inexpensive and widely available antidepressant medications with psychoeducational interventions or targeted psychotherapies to enhance expectancy, it may be possible to significantly improve antidepressant response rates in LLD patients.

Description of Subject Population

Sample #1

Specify subject population

N=130 outpatients with MDD

Number of completers required to accomplish study aims

90

Projected number of subjects who will be enrolled to obtain required number of completers

130

Age range of subject population

60-90

Gender, Racial and Ethnic Breakdown

Gender: We anticipate the sample will be composed of approximately 60% women and 40% men.

Racial/ethnic group: On the basis of previous depression studies conducted in the Adult and Late Life Depression Clinic, it is anticipated that the sample will be composed of approximately 75% Caucasian, 15% African American, and 10% Hispanic subjects.

Description of subject population

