7. Regarding DTI, we will acquire the baseline image B0 and the diffusion weighted images (DWI) in 25 directions. To isolate brain from non-brain tissue, we will apply the DTI software in the FSL analytic package (Analysis Group, FMRIB, Oxford, UK) to the B0 image and use the isolated brain as a mask to define the brain in DWIs. The images will be corrected for eddy current distortions, and then we will fit a diffusion tensor model to the DWI data at each voxel. The tensor model yields a voxel-wise map of 1st/2nd/3rd eigenvectors and eigenvalues, fractional anisotropy (FA), and mean diffusivity across the entire brain. The DT images for all participants will be coregistered by applying affine transformation to a template brain using the B0 images, thereby permitting voxel-wise statistical analyses of the various DTI measures. In addition to the whole-brain voxel-wise statistical analyses, we will perform statistical analyses of the mean FA value within specified ROIs defined using regions of WMH in anatomical MR images for each participant. ROIs with significantly differing DTI measures will be associated with specific pathways in the brain by coregistering the template brain to a DTI atlas (LONI ICBM DTI atlas, cmrm.med.jhmi.edu), which parcellates the brain into 23 functionally meaningful anatomical regions, grouped by brainstem, projection fibers, association fibers, and commissural fibers (described in detail at cmrm.med.jhmi.edu). Finally, within the coordinate space of the template brain, we will perform diffusion tensor tractography from regions within prefrontal cortex to striatum and statistically analyze the various DTI measures at each voxel along these pathways. Statistically significant differences in the DTI measures along these pathways would indicate disruption of anatomical connectivity between regions in the prefrontal cortex and the striatum.

Neuropsychological testing

1. The baseline neuropsychological test battery assembled for this study meets five important criteria that we were striving to achieve (see Table 4): 1) it is short and well tolerated by the elderly (total administration time approximately 40 minutes), 2) it is a reasonably comprehensive assessment of executive functioning, 3) the measures are capable of tapping a range of abilities (minimizes floor and ceiling effects), 4) it comprises standard tests, and 5) it allows for reliable administration by trained technicians.

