Analyses for Specific Aim 1: Hypothesis: Greater ED and WMH will be associated with smaller differences in patient expectancy and antidepressant outcome between the open and placebo-controlled conditions. All tests will be two-sided:  $\alpha=0.05$ , intent-to-treat, with data included for all patients with  $\geq 1$  post-baseline assessment. The primary outcome measure of expectancy (items 2 and 4 of the CES) and antidepressant outcome (24-item HRSD) will be collected at baseline and at weeks 1 through 8. Analysis for expectancy will include all randomized individuals (n=130), analysis for HRSD will drop the n=10 individuals who receive placebo to strictly compare the antidepressant drug outcome of open label vs. double-blind. The hypothesis is addressed by testing the 3-way interaction ( $\beta_8$  in Model 1 below) between baseline ED/WMH, time, and treatment condition. 'ED/WMH' denotes our intention to analyze the effects of ED and WMH individually as well as in combination. The longitudinal mixed effect model (Model 1) will be used where  $Y_{ij}$  is the expectancy or HRSD score for subject  $i$  at  $t_j$  week,  $t_j=1,2,\dots,8$ ,  $y_{i0}$  is expectancy or HRSD at baseline,  $I_i^{TRT}$  is the indicator variable for randomized condition (open label vs. double-blind),  $ED/WMH_i$  is the baseline measure of ED/WMH (see section 3.3.B.6),  $X_i$  includes the randomization stratification variable (i.e., age) and any baseline covariates exhibiting imbalance after randomization,  $b_i$  is a random intercept to account for repeated measures across time within patient, and  $g(t_i)$  is a general function of time to allow for non-linear time trends. We will determine the best way to model  $g(t_i)$  by comparing BIC fit criteria across models including linear, cubic splines, or categorical (i.e., dummy variable) time effects. Model 1 will be fit using PROC GLIMIX in SAS. A significant interaction of  $g(t_i) * I_i^{TRT} * ED/WMH_i$  (corresponding to rejecting the null hypothesis that  $\beta_8 = 0$ ) indicates that the effect of randomized condition on the outcome over time is different by baseline ED/WMH. Because this interaction effect is a function of continuous time and ED/WMH, interpretation will be facilitated by forming contrasts at different fixed values of time (e.g., early vs. late, week 1 vs. week 8) and ED/WMH severity (low vs. moderate vs. high defined by tertiles of baseline ED/WMH distributions). Model 1 will also be used to analyze secondary measures of expectancy (QIDS-SR Expectancy Version) and to test moderator effects of secondary measures of ED and WMH (see sections 3.3.B.5-6.)

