*Analyses for Exploratory Aim:* As described above, DTI data for each subject will yield a voxel-wise map of FA values across the entire brain. Substituting these FA values for ED/WMH in Model 1, we will assess at each voxel whether the FA values differ significantly by randomized condition on expectancy or antidepressant outcome over time. Although Bonferroni correction could be employed to correct for multiple statistical comparisons, it tends to be overly conservative since the sets of FA correlate with one another. Alternatively, we will use statistical analyses based on the theory of Gaussian random fields (GRFs) defined across the entire brain to account for correlations across voxels and to calculate corrected p-values. In addition to GRF-corrected maps, we will also apply the theory of False Discovery Rate (FDR) to control for multiple comparisons while permitting discovery of 5% false positives. Because the method for FDR permits a specified percent of false positive, the method for FDR is statistically more powerful in detecting significant differences in the brain. Our method also allows us to include the use of covariates such as age, sex, and IQ when calculating corrected P-values. Next, we will identify the neural pathways associated with voxels having significant  $g(t_j) * I_i^{TRT} * FA_i$  interactions by coregistering the template DTI brain to the DTI atlas described above. Finally, we will assess the integrity of the frontostriatal and frontolimbic tracts by performing tractography from PFC regions to striatal and limbic areas and assessing whether the significant voxels lie along the fiber tracts.

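### The Exploratory Aim asks about specific tract damage, but the FA analysis has no whole-brain FA term or reference tract, so a diffuse effect could be read as prefrontal-striatal disconnection

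*Protocol*

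**What the plan says.** The protocol (Specific Aims and Hypotheses) sets the Exploratory Aim: to "explore whether specific damage to these pathways is associated with diminished expectancy effects in patients with LLD", where the pathways are the frontostriatal and frontolimbic tracts.

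The SAP (Analyses for Exploratory Aim) gives the model: "Substituting these FA values for ED/WMH in Model 1, we will assess at each voxel". Each fit therefore holds one FA value per patient. The SAP says that the method can "include the use of covariates such as age, sex, and IQ when calculating corrected P-values". Model 1 itself carries age, as the stratification variable, and any baseline covariate found imbalanced after randomization. Corrected maps use Gaussian random fields (GRF) and a 5% false discovery rate (FDR). Voxels with a significant interaction of FA, time and condition are labelled from an atlas, and the last step is "assessing whether the significant voxels lie along the fiber tracts".

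The protocol (Study Procedures, MRI scanning, item 7) describes the tractography as coming "In addition to the whole-brain voxel-wise statistical analyses" and ROI analyses, and states how it will be read: "Statistically significant differences in the DTI measures along these pathways would indicate disruption of anatomical connectivity" between prefrontal and striatal regions.

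**The concern.** The aim is about particular pathways, but the planned test asks only whether FA at a given place moderates the difference between conditions. The SAP itself notes that FA values correlate with one another. If patients differ in overall white-matter integrity, and that is what moderates the expectancy effect, FA in any tract partly stands in for it. A significant prefrontal-striatal tract is then expected whether or not the tract has an effect of its own.

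Checking where the significant voxels lie does not resolve this. Significance in one place and not in another is no test that the two places differ. At stake is the mechanistic conclusion: the protocol's Background names treatments that promote prefrontal-limbic and prefrontal-striatal connectivity as an avenue to explore, and a diffuse effect would not support that targeting.

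**Working it through.** The available text gives no sample size, power or effect size for the Exploratory Aim, so there is no figure of the plan's to reproduce. The check is illustrative.

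**From the documents.** 130 randomized; 120 in the HRSD analysis (130 - 10 on placebo); 90 completers required; two-sided 0.05 (stated for Aim 1); FDR at 5%; an atlas of 23 regions. The number scanned is not given.

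**Assumed.** 100 scanned, 50 per condition; whole-brain FA is the only moderator, with noncentrality 2.83 (about 80% power); each region's FA correlates with whole-brain FA at r; the tract has no effect of its own. The outcome is one standardised change score, a simplification of Model 1.

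**Hand check.** Code condition as +0.5 and -0.5 and standardise FA. The global interaction g satisfies g x sqrt(100)/2 = 2.83, so g = 0.566. Testing the tract alone gives noncentrality

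2.83 x r / sqrt(1 + g² x (1 - r²)/4), with g²/4 = 0.0801.

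- r = 0.5: 1.415 / sqrt(1.0601) = 1.374; power = Phi(1.374 - 1.96) = 28%
- r = 0.7: 1.981 / sqrt(1.0408) = 1.942; power = 49%
- r = 0.8: 2.264 / sqrt(1.0288) = 2.232; power = 61%

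**Simulation of the same set-up, 23 regions.** Share of trials in which the target tract is significant:

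| r | Tract alone, 0.05 | Tract alone, FDR over 23 regions | Global FA and its condition interaction added |
|---|---|---|---|
| 0.5 | 26% | 10% | about 5% |
| 0.7 | 47% | 33% | about 5% |
| 0.8 | 57% | 42% | about 5% |

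The uncorrected rates run slightly below the hand check, which is a large-sample approximation. The last column is also about 5% when the added term is mean FA over the other 22 regions. GRF correction over voxels was not simulated.

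**Which terms are needed.** A second simulation used 90 or 120 patients, a global interaction of 0.6 SD per SD of FA, and r from 0.3 to 0.85, with one tract, uncorrected:

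- Tract alone: 12% to 63% (90 patients) and 16% to 76% (120).
- A comparator tract with the same r: 13% to 64% and 15% to 77%, so significance on the target says nothing about specificity.
- Whole-brain FA added as a main effect only: 12.5% to 62.6% and 16.3% to 75.4%, no improvement.
- Whole-brain FA added with its condition interaction: 4.6% to 5.4%.
- No FA effect anywhere (r = 0.5): about 5% without adjustment, so the excess comes from the shared component.

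**Could the map look specific by chance?** In the 23-region set-up, the target is significant with fewer than 12 regions significant in about 9-19% of trials uncorrected and 5-9% under FDR. With three or fewer regions significant, the uncorrected rate is only 1-2%.

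**The case against.** A reader might infer that a diffuse effect *would* be reported as prefrontal-striatal disconnection. The documents do not support that. The voxel-wise analysis covers the whole brain, the atlas spans brainstem, projection, association and commissural fibres, and overlap with the frontal tracts is checked last. A widespread effect would probably be visible. The protocol's sentence says that altered measures along the tract indicate disruption there; it does not say only there, and diffuse damage includes that tract. The SAP Overview also describes the aim as greater anatomical precision, a looser goal than independence from global FA.

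Uncorrected single-tract rates overstate the risk, because GRF and FDR correction are planned. The covariate list is open-ended, and part of the SAP, including the sections it cites for the ED and WMH measures, is not in the available text, so a global term is not excluded.

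These points limit the concern without removing it. Correction for multiplicity controls chance findings and cannot separate a diffuse from a local association. No stated rule says that a widespread map changes the reading, and the aim's own wording is about specific damage. An open covariate list helps only if the interaction terms are also entered.

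**Conclusion.** The concern holds in a limited form. Nothing in the available text tests whether moderation by prefrontal tract FA exceeds what overall white-matter integrity would produce, so a diffuse effect could be read as prefrontal-striatal disconnection. Even after FDR correction, the illustrative rates stay above 5% across the correlations tried. They rest on assumed correlations, effect size and number scanned, and show direction and range only.

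A second tempting inference is that a non-significant adjusted term would show the effect to be diffuse. It would not, because the adjusted model has much less power for a truly local effect.

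Severity is minor. The point bears on the mechanistic reading of an exploratory aim and leaves Aims 1 and 2 untouched.

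**What to change.** Keep the planned GRF- and FDR-corrected maps. Beside them, report a specificity analysis for the prefrontal tracts, in one of two forms:

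- Add mean white-matter FA outside the tested tract, with the same terms as local FA: main effect, by g(t), by condition, and by g(t) by condition. A main effect alone is not enough.
- Contrast the tract's interaction coefficient directly with that of reference tracts from the same atlas.

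Reword the protocol's DTI sentence so that pathway-specific disruption is claimed only if this analysis supports it. If the unadjusted result is significant and the specificity analysis is not, report a white-matter association whose specificity is undetermined.

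The protocol says that only data analysis is ongoing. The change needs no new data: a summary value per tested tract from each existing FA map and one more set of model terms. The cost is power. For a truly local effect at r = 0.7, noncentrality falls from about 2.8 to 2.8 x sqrt(1 - 0.49) = 2.0, and power from about 78% to 50%. That is why the unadjusted map should stay beside the adjusted result.

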**Data analysis plan. Overview:**

The proposed trial will enroll 130 patients aged 60-90 years and randomize them to open label treatment with escitalopram

(n=60) vs. a double-blind

escitalopram-placebo trial (n=70, with n=60 to escitalopram and n=10 to placebo). Hence, participants in the double-blind condition will not know whether they are receiving drug or placebo. Patients will vary in their baseline severity of ED and WMH burden, which will be measured using the Stroop Color-Word Test and the Fazekas modified Coffey Rating Scale of anatomical MRI images, respectively. Specific Aim 1 focuses on determining whether differences in expectancy and depression outcomes found over time between the two randomized conditions are *moderated* by baseline ED and WMH measures (i.e., whether more severe ED and/or WMH are associated with smaller differences between the open and placebo-controlled conditions). Specific Aim 2 investigates whether poor antidepressant outcome (regardless of randomized condition) is associated with more severe baseline ED and WMH burden, and whether this association is *mediated* by decreased patient expectancy. In the Exploratory Aim, we are interested in using DTI to explore with greater anatomical precision the white matter damage associated with smaller differences in patient expectancy and antidepressant outcome between the open and placebo-controlled conditions.

Before the specific statistical techniques are applied, we will examine all variables at all time points for illegitimate values, outliers, and inconsistencies. The distribution of demographic variables, rater-administered and self-report measures will be examined and described in terms of means, standard deviations, minima, and maxima for continuous variables, and proportions for categorical variables. Missing data: We will make every effort to obtain all data. The longitudinal mixed modeling described below imputes unobserved time points using observed data from the individual combined with the overall trend. Inferences are valid if missing data are missing at random (MAR). MAR assumptions cannot be verified. A 2010 national expert panel recommended sensitivity analyses for the impact of missing data via pattern mixture models, which we will conduct (e.g., by investigating robustness of results to perturbations of assumed values for missing data within clinically plausible ranges).

Analyses for Specific Aim 1: Hypothesis: Greater ED and WMH will be associated with smaller differences in patient expectancy and antidepressant outcome between the open and placebo-controlled conditions. All tests will be two-sided:  $\alpha=0.05$ , intent-to-treat, with data included for all patients with  $\geq 1$  post-baseline assessment. The primary outcome measure of expectancy (items 2 and 4 of the CES) and antidepressant outcome (24-item HRSD) will be collected at baseline and at weeks 1 through 8. Analysis for expectancy will include all randomized individuals (n=130), analysis for HRSD will drop the n=10 individuals who receive placebo to strictly compare the antidepressant drug outcome of open label vs. double-blind. The hypothesis is addressed by testing the 3-way interaction ( $\beta_8$  in Model 1 below) between baseline ED/WMH, time, and treatment condition. 'ED/WMH' denotes our intention to analyze the effects of ED and WMH individually as well as in combination. The longitudinal mixed effect model (Model 1) will be used where  $Y_{ij}$  is the expectancy or HRSD score for subject  $i$  at  $t_j$  week,  $t_j=1,2,\dots,8$ ,  $y_{i0}$  is expectancy or HRSD at baseline,  $I_i^{TRT}$  is the indicator variable for randomized condition (open label vs. double-blind),  $ED/WMH_i$  is the baseline measure of ED/WMH (see section 3.3.B.6),  $X_i$  includes the randomization stratification variable (i.e., age) and any baseline covariates exhibiting imbalance after randomization,  $b_i$  is a random intercept to account for repeated measures across time within patient, and  $g(t_i)$  is a general function of time to allow for non-linear time trends. We will determine the best way to model  $g(t_i)$  by comparing BIC fit criteria across models including linear, cubic splines, or categorical (i.e., dummy variable) time effects. Model 1 will be fit using PROC GLIMIX in SAS. A significant interaction of  $g(t_i) * I_i^{TRT} * ED/WMH_i$  (corresponding to rejecting the null hypothesis that  $\beta_8 = 0$ ) indicates that the effect of randomized condition on the outcome over time is different by baseline ED/WMH. Because this interaction effect is a function of continuous time and ED/WMH, interpretation will be facilitated by forming contrasts at different fixed values of time (e.g., early vs. late, week 1 vs. week 8) and ED/WMH severity (low vs. moderate vs. high defined by tertiles of baseline ED/WMH distributions). Model 1 will also be used to analyze secondary measures of expectancy (QIDS-SR Expectancy Version) and to test moderator effects of secondary measures of ED and WMH (see sections 3.3.B.5-6.)

Analyses for Specific Aim 2: Hypothesis: ED and WMH will be associated with decreased change in depressive symptoms, and this association will be mediated by a decreased contribution of expectancy to antidepressant outcome. The first part of this hypothesis will be tested using a longitudinal mixed effect for HRSD scores as in Model 1 but only including predictors that do not involve randomized condition, i.e.  $\beta_0, \beta_1, \beta_2, \beta_6, \beta_9$ . The tests of interest are the main effect for ED/WMH and its interaction with time (i.e.  $\beta_4$  and  $\beta_6$ ). After having established an overall effect of ED and/or WMH on depression outcome (i.e., HRSD), we will test

$$\text{MODEL 1: } Y_{ij} = \beta_0 + \beta_1 y_{i0} + \beta_2 g(t_j) + \beta_3 I_i^{TRT} + \beta_4 ED/WMH_i + \beta_5 g(t_j) * I_i^{TRT} + \beta_6 g(t_j) * ED/WMH_i + \beta_7 I_i^{TRT} * ED/WMH_i + \beta_8 g(t_j) * I_i^{TRT} * ED/WMH_i + \beta_9 X_i + b_i + \epsilon_{ij}$$

[figure not shown]

Figure 5. Mediation of the relationship between ED/WMH and antidepressant outcome by a loss of expectancy effects.

$\beta_4$ ,

expectancy as a mediator of the relationships (see Figure 5). To be a mediator we must establish that expectancy is affected by ED/WMH and that it influences antidepressant outcome controlling for ED/WMH. In order to ensure time order of the mediator (expectancy) occurring prior to the depression outcome (HRSD), we will use early change in expectancy (i.e., from baseline to week 1) as the primary measure for the mediator. A model with week 1 expectancy as the outcome and ED/WMH as the primary predictor, controlling for baseline covariates, will be used to estimate path a in Figure 5. To estimate path b in Figure 5, the same longitudinal mixed effect model described above with the addition of week 1 expectancy as a predictor will be used. The mediation effect is estimated by taking the product of the estimates for a and b and using the bootstrap method to obtain standard errors, confidence intervals, and the test for statistical significance. Recent developments in mediation analysis suggest the need for sensitivity analyses to explore potential impact of unmeasured confounders. We will perform these sensitivity analyses with the new mediation R package that provides a range of plausible results that may have been obtained under different assumptions about unmeasured confounders.

*Analyses for Exploratory Aim:* As described above, DTI data for each subject will yield a voxel-wise map of FA values across the entire brain. Substituting these FA values for ED/WMH in Model 1, we will assess at each voxel whether the FA values differ significantly by randomized condition on expectancy or antidepressant outcome over time. Although Bonferroni correction could be employed to correct for multiple statistical comparisons, it tends to be overly conservative since the sets of FA correlate with one another. Alternatively, we will use statistical analyses based on the theory of Gaussian random fields (GRFs) defined across the entire brain to account for correlations across voxels and to calculate corrected p-values. In addition to GRF-corrected maps, we will also apply the theory of False Discovery Rate (FDR) to control for multiple comparisons while permitting discovery of 5% false positives. Because the method for FDR permits a specified percent of false positive, the method for FDR is statistically more powerful in detecting significant differences in the brain. Our method also allows us to include the use of covariates such as age, sex, and IQ when calculating corrected P-values. Next, we will identify the neural pathways associated with voxels having significant  $g(t_j) * I_i^{TRT} * FA_i$  interactions by coregistering the template DTI brain to the DTI atlas described above. Finally, we will assess the integrity of the frontostriatal and frontolimbic tracts by performing tractography from PFC regions to striatal and limbic areas and assessing whether the significant voxels lie along the fiber tracts.

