Consistent with the above model, cognitively intact patients with LLD appear to experience large expectancy effects during antidepressant treatment. We have shown that LLD patients enrolled in comparator-type studies, who are assured of receiving active medication for their condition, have medication response rates nearly double those of LLD patients enrolled in placebo-controlled studies, who are aware they may be receiving placebo.¹ However, the ability to generate expectancy effects appears to be attenuated in LLD patients with significant WMH: we found in analyses of a large antidepressant trial for LLD that more severe WMH was associated with decreased response to placebo.¹⁵ In addition, a prospective study conducted preliminary to this application randomized depressed patients to receive the same antidepressant medication in “high expectancy” vs. “low expectancy” experimental conditions.¹⁶ Randomization to the high as opposed to low expectancy condition resulted in increased expectancy of improvement and greater change in depressive symptoms over 8 weeks for patients < 60 years old. This was not true for patients ≥ 60 years old, who experienced little expectancy change and no treatment benefit in the high vs. low expectancy conditions.

To determine whether decreased antidepressant medication response in LLD patients with ED and WMH is

caused by a loss of expectancy effects, we will evaluate 130 outpatients with LLD at baseline to determine their degree of ED (interference score on Stroop Color-Word Test¹⁷), WMH burden (severity score on Fazekas modified Coffey Rating Scale¹⁸ derived from anatomical MRI), and white matter tract integrity (using diffusion tensor imaging [DTI]). Building on work from my K23 Award, we will manipulate participants' expectancy of improvement in an 8-week duration antidepressant trial by randomizing them between open administration of escitalopram or duloxetine (i.e., high expectancy) and placebo-controlled administration of escitalopram or duloxetine (i.e., low expectancy). The difference in antidepressant response observed between open and placebo-controlled medication treatment is a measure of the expectancy contribution to outcome, which is substantial in younger depressed adults¹⁶ but we hypothesize will be diminished in LLD patients with ED and WMH.

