 - a. Subjects in the Open Group will be informed: “You have been randomly assigned to the open group of the study. This means that there is a 100% chance you will receive the antidepressant medication escitalopram [or duloxetine] for the duration of the study. Escitalopram [or duloxetine] has been proven effective for the treatment of depression in patients like you. You will not be receiving any placebo pills for the duration of the study. While you are aware that you are receiving actual antidepressant medication and not placebo, some of the staff members seeing you do not know whether you are taking escitalopram [or duloxetine] or placebo. If it can be avoided, please do not reveal to anyone in the study what group you have been assigned to.” At the time of their entry into the study, patients will be started on escitalopram 10mg per day, which will be continued for four weeks. If at the end of that time patients do not meet remission criteria (HRSD < 11) or the patient continues to report depressive symptoms, is tolerating the medication well, and wishes to try a higher dose, the dose will be increased to 20mg escitalopram for the remainder of the study. Subjects who have previously not responded to or not tolerated escitalopram will be allowed to receive duloxetine. Subjects will receive duloxetine 30mg for 1 week, then if they do not meet remission criteria or the patient continues to report depressive symptoms, is tolerating the medication well, and wishes to try a higher dose, will increase to 60mg for 4 weeks, and then if they still do not meet remission criteria or the patient continues to report depressive symptoms, is tolerating the medication well, and wishes to try a higher dose, will increase to 90mg for final 3 weeks. The first choice is for subjects to receive escitalopram, and they will only receive duloxetine if they have previously failed or not tolerated escitalopram.
 - b. Subjects in the Placebo-controlled Group will be randomized unequally (6:1) to escitalopram [or duloxetine] vs placebo. They will be informed: “You have been randomly assigned to the placebo-controlled group of the study. This means that there is a chance you will receive the antidepressant

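### Aim 1 is decided by β8 alone, so ED/WMH moderation present by week 1 and then sustained does not count; the concern is plausible for expectancy and minor for HRSD unless most moderation is early

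*SAP*

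**What the plan says.** The protocol (Specific Aims and Hypotheses) states Hypothesis 1 as "Greater ED and WMH will be associated with smaller differences in expectancy and antidepressant outcome between conditions". The SAP overview puts the same question as "whether more severe ED and/or WMH are associated with smaller differences between the open and placebo-controlled conditions".

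Under Analyses for Specific Aim 1, the SAP says that "The hypothesis is addressed by testing the 3-way interaction" between baseline ED/WMH, time and condition, and identifies this term as β8. The outcome is modelled at weeks 1 to 8, the baseline value is a covariate, and there is a random intercept per patient. The form of g(t) is linear, spline or categorical, chosen by BIC. Model 1 also contains β7, the condition-by-ED/WMH term, but no test or decision is attached to it. Contrasts at chosen weeks and ED/WMH levels are planned, introduced by the words "interpretation will be facilitated by forming contrasts at different fixed values of time".

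For the first part of Aim 2 the SAP names both components: "The tests of interest are the main effect for ED/WMH and its interaction with time".

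**The concern.** The test and the hypothesis concern different quantities. The hypothesis is about the size of the open versus placebo-controlled difference at different levels of ED/WMH. β8 is about whether that pattern changes between week 1 and week 8. An effect that arises between baseline and week 1 and then holds satisfies the hypothesis but leaves β8 at zero.

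An early effect is plausible for expectancy. Patients in both groups are told their condition when it is assigned (protocol, Clinical study, items 1a and 1b; the open script begins "You have been randomly assigned to the open group of the study"), before any response that Model 1 analyses under treatment.

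Two wrong conclusions are possible. A null β8 could be taken as absence of moderation when moderation is large and steady. A significant β8 could be taken as support when moderation was present early and had gone by week 8.

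**Working it through.** **Inputs from the documents.** Response weeks 1 to 8, baseline as covariate, random intercept, two-sided α = 0.05 (SAP, Specific Aim 1 and Model 1). Planned numbers: expectancy 60 open vs 70 placebo-controlled; HRSD 60 vs 60 after the 10 placebo patients are dropped.

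**Assumptions.** The supplied text gives no effect size, correlation or power for Aim 1, so there is no plan figure to reproduce. I assume a peak moderation d, in residual SDs of the weekly score per SD of ED/WMH; a between-week correlation ρ of 0.4 to 0.8; a moderator independent of condition; and complete data.

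**Step 1, structure (no assumptions needed).** In Model 1 the condition difference at week t is β3 + β5·g(t) + [β7 + β8·g(t)]·ED/WMH. Moderation is therefore M(t) = β7 + β8·g(t). If M(t) = c for every t from 1 to 8, then β7 = c and β8 = 0. The β8 test then rejects at its nominal 5% for any c, any ρ and any of the three forms of g.

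**Step 2, precision with linear g.** Let I = n1·n2/(n1+n2): 60·70/130 = 32.31 for expectancy and 60·60/120 = 30 for HRSD. Since Σ(t − 4.5)² = 42:
- Var(β8) = (1 − ρ)/(42·I)
- Var(weeks 1-8 average) = [ρ + (1 − ρ)/8]/I
- Var(week 8) = Var(average) + 3.5²·Var(β8)

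Example: expectancy, d = 0.5, ρ = 0.6. SE(β8) = √(0.4/(42·32.31)) = 0.0172 and SE(average) = √(0.65/32.31) = 0.142.
- Sustained: β8 = 0, power 5.0%. Average = 0.5, z = 3.53, power 94.1%. Joint test: noncentrality 3.53² = 12.4 on 2 df, power 89.4%.
- Linear growth from week 0: β8 = 0.5/8 = 0.0625, z = 3.64, power 95.4%. Average = 0.0625·4.5 = 0.281, z = 1.98, power 50.9%. Joint noncentrality 3.64² + 1.98² = 17.2, power 96.8%.

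**Step 3, range over ρ = 0.4 to 0.8.** Expectancy, 60 vs 70, d = 0.5, linear g; two-sided rejection in %.

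| Moderation over weeks 1-8 | β8 | Joint β7 = β8 = 0 | Time average | Week 8 |
|---|---|---|---|---|
| Sustained from week 1 | 5 | 81-97 | 88-98 | 86-94 |
| Plateau at week 2 | 17-40 | 87-96 | 84-97 | 91-97 |
| Plateau at week 4 | 67-99 | 97 to >99 | 72-92 | 94-98 |
| Linear growth from week 0 | 84 to >99 | 93 to >99 | 42-64 | 86-94 |
| Full at week 1, half by week 8 | 40-84 | 86-93 | 65-87 | 33-42 |
| Full at week 1, zero by week 8 | 93 to >99 | 95 to >99 | 35-54 | 5 |

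HRSD, 60 vs 60, same settings, β8 then joint:
- all present at week 1: 5, then 78-95
- half present at week 1, rising to full: 37-81, then 84-91
- linear growth from week 0: 82 to >99, then 91 to >99

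**Step 4, sensitivity (sustained, expectancy).**
- Smaller effects, linear g: joint 49-74% at d = 0.35 and 19-30% at d = 0.2.
- Categorical g, d = 0.5: joint 58-86%, time average 88-98%, week 8 about 81%.
- Assumed dropout of 10-28%, completely at random, d = 0.5, linear g: joint 80-96%.
- β8 stays at 5% in each of these settings.

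**The case against.** The strongest reply is that the SAP meant a trajectory. Its overview speaks of differences over time, and the Aim 1 section reads a significant β8 as a condition effect over time that varies with ED/WMH. That reading is available. But Hypothesis 1 and the overview's own gloss ask only for smaller differences. With baseline as a covariate, β8 also does not measure change from baseline: whatever arises before week 1 falls outside it.

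The planned fixed-time contrasts do contain β7, so a sustained effect could appear in output already planned. This stands, and it limits the harm. The contrasts are there for interpretation, however, and do not decide the aim.

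The size of the loss depends on the profile. The 5% needs moderation that is flat from week 1, and nothing in the documents says that it will be flat. For HRSD the protocol describes the pilot result in patients under 60 as a condition that "resulted in increased expectancy of improvement and greater change in depressive symptoms over 8 weeks". If HRSD moderation builds steadily, β8 keeps most of its power.

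A reader might infer more from the Aim 2 text, where "we will use early change in expectancy (i.e., from baseline to week 1) as the primary measure for the mediator", namely that the plan itself expects expectancy moderation by week 1. The documents do not support that. The SAP gives time order as the reason for the choice, and the path concerned runs from ED/WMH to week-1 expectancy without involving condition. Nor does the SAP say that a null β8 will be reported as no moderation; that is a risk of misreading.

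**Conclusion.** The mismatch is real and should be fixed. It follows from the structure of Model 1: sustained moderation gives β8 = 0 and a 5% rejection rate at any effect size, and fading moderation can give a rejection. β8 alone therefore cannot settle Hypothesis 1 in either direction.

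For expectancy the concern is plausible because condition is disclosed at assignment, but the documents do not say when moderation should appear. For HRSD it is minor unless most of the moderation is present by week 1. Every power figure other than the 5% rests on assumed effect sizes and correlations. It would be too strong to infer that the Aim 1 test is generally without power: for moderation that plateaus at week 4 or grows linearly, β8 has 67% to over 99% power under the expectancy settings tabulated.

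**What to change.** Keep Model 1 and the BIC-chosen g.

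1. Base the Aim 1 moderation test on the joint null β7 = β8 = 0. Unlike β7 alone, this does not depend on how time is coded.
2. Take direction from the week-specific contrasts already planned, plus a time-averaged contrast over weeks 1 to 8, each with a 95% CI. If one directional claim is wanted, the sponsor should prespecify a single contrast and use it without first requiring the joint test. Requiring both can only lose power: for the week-8 contrast with categorical g, sustained moderation and d = 0.5, 55-74% against about 81%. The choice has a price either way. Week 8 is weak for partly fading moderation (33-42% in the table), and the time average is weak for late-growing moderation (42-64%).
3. Do not report a null β8 as no moderation.
4. Make the change by a dated amendment that states what outcome data had been seen, and report the original β8 result alongside. The protocol's continuation section says only analysis remains and already describes overall response and remission rates. If outcomes by condition or by ED/WMH had been examined, label the new test supportive.

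The cost is one joint contrast and one time-averaged estimate from the same model and data. The joint test spends one more degree of freedom. Its largest loss found against β8 is about 7.5 points (62% vs 55%: 60 vs 60, linear g, no moderation at week 1 then linear growth, d = 0.2, ρ = 0.8).
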